6.1.4. Mediation Modeling

For some of the analyses described above we will need to carefully assess the potential effects of mediators on the relationships we are examining. We will use mediation models as described by Baron & Kenny⁽¹⁾ in which a series of ANCOVA models are fit regressing: 1) outcome on exposure (Model 1); 2) mediator on exposure (Model 2); and 3) outcome on both mediator and exposure (Model 3). A change in the estimate of the exposure effect from Model 1 to Model 3 is evidence of mediation. We will use bootstrap methods for significance testing of the mediation effect and for calculating confidence intervals⁽²⁾.

What is particularly exciting about using the SEARCH Cohort study is that potential mediator data will be measured at least at two time points. For instance, we can examine potential differences in access to care (a potential mediator) at particular points in time in relation to outcomes of interest. In addition we can form models that incorporate several potential mediators simultaneously (e.g., access to care and physical activity). Procedures, such as examining eigenvalues, discussed in Belsley, Kuh, and Welch ⁽³⁾ and Kleinbaum, Kupper and Muller ⁽⁴⁾ will be used to identify problems with multicollinearity and appropriate steps will be taken to reduce the problem.

6.1.5. Missing Data Considerations

We utilize the sequential data collection of the SEARCH protocol to statistically adjust for potential selection bias related to response rates or other reasons for missing data. Variables determined to predict loss to follow-up will be included in our predictive models in order to satisfy the conditions for the data to be considered "Missing at Random" (MAR)⁽⁵⁾. Estimation techniques such as maximum likelihood will be used to estimate parameters. If the MAR assumption is untenable, one must assume that "informative censoring" has occurred. For example, biased estimates can result if participants with adverse experiences are more likely to withdraw (or, conversely, tend to be relatively less likely to withdraw). A growing body of literature describes two alternative approaches to handle this potential problem: explicit modeling of the censoring mechanisms $^{(6-12)}$ and pattern-mixture models $^{(13)}$. We have experience with these approaches for handling non-ignorable non-response and will analyze the data using several of these methods which incorporate varying assumptions about the missing observations ⁽¹⁴⁾. This will provide useful information to allow us to understand the potential limitations we may have to interpret results in the presence of informative censoring.

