De-duplication: Duplicates will be identified using both electronic files and manually, both within and between case sources, using the name or initials, gender, date of birth, ethnicity, zip code, or other available information, in keeping with HIPAA requirements to use the least amount of PHI in conducting research. The number of duplicates identified will be used to estimate completeness of ascertainment with the capture-recapture method among the geographic centers.

Systematic re-ascertainment: A systematic case re-ascertainment process will be conducted in 2012 for cases incident in 2006-2010 and in 2014 for 2008-2012 cohorts. The purpose of re-ascertainment is to assure as complete ascertainment of diabetes cases as possible, especially those with T2D, who, due to different care patterns, we theorize are more likely to be missed by the SEARCH network prior to the close of the registration window. Additional cases will be registered with the center and the CoC with a flag to indicate that they were registered outside of the standard window.

Case Registration: Cases that are valid, eligible and unique will be registered by the center with information being uploaded to the CoC. Minimal information about the participant (age, gender, race/ethnicity, type of diabetes reported by clinician, center, date of diagnosis, zip code or county of residence, and birth date) will be uploaded to the CoC website in order to protect confidentiality. Names and addresses are not provided to the CoC. In cases where duplicates and cases that are not valid or eligible are identified at a later date, they will be unregistered by both the local center and the CoC.

Collection of Core Variables: A minimum amount of demographic and clinical information is needed for all registered cases in order for the study to be able to provide population-based rates of diabetes mellitus by age, gender, diabetes type and race/ethnicity for the entire population of cases. This information is also critical in assessing possible response bias to the in person research visit. This information is called "core" information. The main sources of core data are medical records and the initial participant survey and are described in Table 5 - 1.

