6.1.2. Prevalence Estimation

Some of the outcomes of interest will not have been measured during SEARCH 1 or 2, such as outcomes including retinopathy and neuropathy. Therefore, prevalence of these outcomes will be estimated. Models to evaluate cross-sectional associations of risk factors will use logistic regression and will proceed as described above to account for potential confounding or effect modification.

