6.1.3. Longitudinal Models

All participants in the SEARCH Cohort Study will have already had at least one inperson visit during SEARCH 1 and 2, and ~75% of the 2002-2005 incidence cases have at least 2 in-person visits per the SEARCH 2 protocol. Since SEARCH 2 also included longitudinal data (there are over 2000 SEARCH participants already with at least one follow-up visit), our team developed a plan for modeling longitudinal data. Specifically, we will use longitudinal mixed effects analysis of covariance models that always include duration of diabetes as a time-varying covariate. This approach correctly models the varying durations of disease prior to the initial SEARCH in-person visit, and the varying

Section 6B - Statistical Considerations (Phase 3 - 12/2010) Cohort Study

durations of time allowed via the SEARCH data collection windows between the initial and subsequent visits.

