For analysis of longitudinal discrete outcomes (e.g. transfer of care from a pediatric to adult provider), we will use the generalized estimating equation (GEE) approach to fit logistic or log-linear models that account for the dependency between repeated measures. GEE techniques allow estimation of model parameters and their standard errors from longitudinal data having continuous and categorical responses and potentially missing observations. An advantage of this technique is that the assumptions required are weaker than those of maximum likelihood techniques: one need not specify the distribution of the dependent variable, just the relationships between the marginal mean and variance, and between the marginal mean and covariates.

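### The missing-data rule enters predictors of loss as covariates, which does not make GEE valid under MAR, does not standardise an attendee prevalence, and may take mediators into total-effect race models

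*Protocol*

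**What the plan says.** All references are to the Protocol.

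- **Rule for loss (Section 6B, 6.1.5).** "Variables determined to predict loss to follow-up will be included in our predictive models in order to satisfy the conditions for the data" to be treated as MAR. Then: "Estimation techniques such as maximum likelihood will be used to estimate parameters". If MAR is untenable, explicit models of the censoring mechanism and pattern-mixture models are to be used. The predictors of loss are not listed.
- **Continuous longitudinal outcomes (6.1.3).** "we will use longitudinal mixed effects analysis of covariance models that always include duration of diabetes as a time-varying covariate".
- **Discrete longitudinal outcomes (6.1.3).** Here "we will use the generalized estimating equation (GEE) approach to fit logistic or log-linear models that account for the dependency between repeated measures". The example given is transfer from a pediatric to an adult provider. The section adds: "GEE techniques allow estimation of model parameters and their standard errors from longitudinal data having continuous and categorical responses and potentially missing observations". No weighting, imputation or working correlation is named.
- **Retinopathy and neuropathy (6.1.2).** These were not measured in SEARCH 1 or 2, so "prevalence of these outcomes will be estimated". Logistic regression is used for cross-sectional associations.
- **Mediation (6.1.4).** Model 1 regresses outcome on exposure, and Model 3 adds the mediator. Mediation is read from the change in the exposure effect between the two.
- **Race and care (Section 4B).** Research Question 3.2 asks whether barriers to care and quality of care explain differences between minority and non-Hispanic white youth. Section 4.2.1.3 names barriers to care as an example of a mediator linked to socio-cultural factors such as race/ethnicity.
- **Attendance (Section 5B, 5.1.1).** The goal is an 80% clinic visit rate, with a further 10% by telephone or internet survey.

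**The concern.** The plan has one remedy for MAR loss: condition on the predictors of loss in the outcome model and rely on an estimator such as maximum likelihood. That suits the mixed models. It does not carry over to three other planned analyses.

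1. **GEE for discrete outcomes.** GEE is not a likelihood method. When attendance depends on an earlier value of the outcome, the data can be MAR and likelihood remains valid, but standard GEE is in general biased. Entering covariates in the mean model removes only the part of the loss that those covariates explain.
2. **Prevalence.** A covariate in a logistic model gives a conditional association. It does not, by itself, turn the proportion among attendees into the proportion in the eligible cohort.
3. **Race effects.** Entering a variable because it predicts loss also changes the effect being estimated. If that variable lies between race and outcome, Model 1 no longer estimates the total effect.

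At stake are the discrete longitudinal results, the first cohort-wide retinopathy and neuropathy prevalences, and the share of the race difference attributed to care.

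**Working it through.** The plan states no bias figure, so there is none to reproduce. The numbers below are illustrations on assumed loss mechanisms; only the 80% attendance comes from the plan.

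**A. GEE with outcome-dependent attendance**

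Assumed: prevalence 20% at visit 1; 60% of those affected stay affected; 10% of the others become affected; attendance at visit 2 is 60% in those affected at visit 1 and 85% in the others.

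- True prevalence at visit 2: 0.2×0.6 + 0.8×0.1 = 0.20.
- Overall attendance: 0.2×0.60 + 0.8×0.85 = 0.80.
- *Independence working correlation.* GEE returns the attendee mean: (0.2×0.60×0.6 + 0.8×0.85×0.1)/0.80 = (0.072 + 0.068)/0.80 = 0.175.
- *Exchangeable working correlation.* With one mean per visit, the equations give p1 = 0.20 and p2 = 0.175 − α·√(v2/v1)·(m1 − p1). Here m1 = 0.12/0.80 = 0.15 is the visit 1 prevalence among attendees, and v1, v2 are the binomial variances p(1 − p). The full-data correlation is (0.12 − 0.04)/0.16 = 0.50. Estimated from attendees by the usual moment formula, with the scale parameter estimated, α is 0.423. Then p2 = 0.175 + 0.423×0.993×0.05 = 0.196.

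The bias is therefore 2.5 points under independence and about 0.4 points under exchangeable correlation. Most of it disappears with a sensible working correlation, but not all, because that correlation is itself estimated from selected pairs. Weighting each attendee by 1/0.60 or 1/0.85 returns 0.20.

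**B. The same question with a covariate that also drives loss**

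Simulation of 40,000 subjects with two binary visits, 35% minority (the split in Section 6B, 6.2.1) and about 20% loss. Assumed: low socio-economic status (SES) in 20% of non-Hispanic white and 50% of minority youth, and a loss odds ratio of 2 for low SES. SES is entered in the GEE models, as 6.1.5 would require; the weights use the known attendance probabilities.

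| Loss odds ratio for a positive earlier outcome | True visit 2 prevalence | GEE, independence | GEE, exchangeable | Weighted GEE |
|---|---|---|---|---|
| 1 (loss depends on SES only) | 29.5% | 29.5% | 29.4% | 29.5% |
| 2 | 29.2% | 28.3% | 29.0% | 29.0% |
| 4 | 29.3% | 27.9% | 29.1% | 29.4% |

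When loss depends only on a modelled covariate, the rule works. When it also depends on the earlier outcome, 0.9 to 1.4 points of bias remain under independence and about 0.2 under exchangeable correlation.

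**C. Race effect**

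In the same simulation, before any loss, entering SES moves the visit 2 race odds ratio from 1.49 to 1.25 (first row), 1.50 to 1.26 (second) and 1.42 to 1.18 (third). This is a change from a total to a conditional effect, not missing-data bias. In 6.1.4 it would fall on Model 1, so the Model 1 to Model 3 change would omit whatever the loss predictor carries.

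**D. Prevalence**

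Retinopathy and neuropathy have no earlier value, so a likelihood model has no earlier outcome to borrow from. The attendee proportion equals the cohort proportion only if attendance is unrelated to the outcome. Removing the part of the selection explained by baseline variables needs weighting, or averaging of model predictions over the whole eligible cohort. 6.1.2 states neither.

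**The case against.** - **The size depends on the working correlation.** The plan asks for GEE that accounts for dependency between visits, so independence is not the natural reading and the 2.5-point figure is an upper illustration. This stands: about 0.4 points is the fairer figure for that example.
- **A reader might infer that all MAR loss goes uncorrected.** The documents do not support that. Continuous outcomes use mixed models, covariate-driven loss is handled, and likelihood is named only as an example. That GEE will be unweighted is inferred from silence.
- **A reader might infer that 6.1.3 has the assumptions the wrong way round** where it says that "the assumptions required are weaker than those of maximum likelihood techniques". It does not. The sentence goes on to explain that the outcome distribution need not be specified, which is correct and is not a statement about missing data.
- **A reader might infer that race effects will be over-adjusted.** The predictors of loss are unnamed, 6.1.1 builds models in stages, and Research Question 3.3 itself asks for contrasts independent of socio-cultural factors. Over-adjustment is a conditional risk, real for Question 3.2 and Model 1.
- **The 80% rate does not apply to every outcome.** Transfer of care is collected by questionnaire, and surveys are meant to raise inclusion to 90%, so its exposure to loss is smaller.
- **Sensitivity analyses are planned.** They are, but for the case where MAR is untenable. They do not repair a GEE analysis when MAR holds.
- **The choice of weights or imputation can be left to a SAP.** True, but 6.1.5 fixes where the predictors of loss go, and that is the part to change.

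**Conclusion.** The point holds in limited form. The stated rule suits likelihood models for continuous outcomes and loss that depends only on modelled covariates. It does not make GEE valid when attendance depends on earlier outcomes, does not standardise the retinopathy and neuropathy prevalences to the eligible cohort, and would weaken Model 1 for Question 3.2 if a loss predictor is a mediator.

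The size is modest and unknown. In the illustrations the GEE bias is 0.2 to 0.4 points of prevalence under exchangeable correlation and 0.9 to 2.5 points under independence. These figures rest on assumed loss mechanisms that the protocol does not give. They do not apply to retinopathy or neuropathy, which have no earlier measurement and are not analysed by GEE; for those the size of any bias cannot be derived from the document. A cheap improvement is available and should be taken.

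**What to change.** Amend Section 6B as follows.

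1. **6.1.5.** Use predictors of loss as weighting or auxiliary variables, not as automatic covariates in the outcome models. Keep those that are mediators out of total-effect race models, including Model 1 of 6.1.4. Question 3.3 may still adjust for socio-cultural factors, because it asks for that.
2. **6.1.3, discrete outcomes.** Name a method valid under MAR: GEE weighted by inverse probability of attendance, multiple imputation, or a likelihood-based mixed logistic model.
3. **6.1.2.** Weight attendees to the 3,699 eligible participants, using the baseline-visit data already held. Weighting to all registered cases can be an optional sensitivity analysis, since it targets a wider population than the Cohort Study defines. Core variables exist for that purpose: Section 5A, 5.1.2 says of them, with regard to the registry's own visit, "This information is also critical in assessing possible response bias to the in person research visit".
4. Keep the censoring-mechanism and pattern-mixture models as sensitivity analyses.

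The cost is wording, some programming and slightly wider intervals. No data collection changes.

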6.2. POWER ANALYSIS

Based on our calculations from SEARCH 1 and 2 we anticipate that at least 3,288 subjects will participate in the SEARCH Cohort Study in-person visit, and therefore the calculations below use that sample size as the starting value for estimating power and detectable differences.

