5.1. SEARCH COHORT STUDY VISIT METHODS

5.1.1. Eligibility and Anticipated Sample Size

Individuals registered in the SEARCH cohort with a diagnosis of non-gestational diabetes in incident years 2002-2005, 2006 and 2008 and who completed a SEARCH baseline inperson visit in one of the SEARCH clinical centers will be eligible for the new SEARCH Cohort Study once they have had diabetes for at least 5 years. We will determine an algorithm that optimizes duration of disease over the data collection years of the Cohort Study, considering both diagnosis year and the timing of the most recent SEARCH visit during the SEARCH 2 protocol. We anticipate that the average duration of diabetes will be 8-9 years (range 6-14 yrs diabetes duration), and the average age of participants at the time of the SEARCH Cohort Visit will be about 20 years (range 8-32 yrs old). Our goal is to have 80% of eligible members of the cohort attend the proposed SEARCH Cohort Study visit, for a total of 3145 participants with a Cohort Study visit.

Of the 20% not attending the research clinic visit, an additional 10% will be participate by completion of surveys by telephone or internet, for a total of 90% inclusion or 3550 individuals. Based on proportions of youth in sub-groups of diabetes type and race/ethnicity, the anticipated numbers and characteristics of anticipated participants in the SEARCH Cohort Study data collection are displayed in Table 5-1.

Table 5-1. Anticipated Sample Size and Characteristics: SEARCH Cohort Study (2002 - 2006, 2008)												
	S	SC	0	Н	CO	C	C.	A	W	/A	All	
Туре	80%	90%	80%	90%	80%	90%	80%	90%	80%	90%	80%	90%
Race/Ethnicity												
Type 1												
NHW	405	456	386	434	711	800	98	110	410	461	2010	2261
Other	175	197	58	65	188	211	185	209	94	106	700	788
Type 2												
NHW	38	42	30	34	16	17	7	8	16	18	107	119
Other	106	120	42	47	79	95	83	97	18	23	328	382
ALL	724	815	516	580	994	1123	373	424	538	608	3145	3550

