6.2.1. Incidence Rate Estimation

To estimate power for this component we first had to estimate the proportion of participants who would be free of the condition at their initial in-person visit during SEARCH 1 and 2. Table 6-1 shows the expected sample sizes available for comparing incidence rates between subgroups under two scenarios: 1) proportion in subgroups are 86% versus 14% (the proportions of T1D and T2D), and 2) proportion in subgroups are 65% versus 35% (the proportions of NHW and all others).

 Table 6-1: Expected Sample Sizes Available for Comparing Incidence Rates between Subgroups

 Under Two scenarios

	Scenario 1		Scena	ario 2		
Outcome (% of participants free of	Subgroup A	Subgroup B	Subgroup A	Subgroup B		
condition at initial SEARCH visit)	(86%)	(14%)	(65%)	(35%)		
	Expected n	Expected number of participants free of outcome at initial visit				
Hypertension (92%)	2504	423	1893	1019		
Obese (bmi-z \ge 95 th %ile) (76%)	2069	349	1564	842		
High LDL (≥ 100) (57%)	1511	262	1173	631		
High ACR (≥30 (90%)	2450	414	1852	997		
Hypoglycemia in last 6 months (91%)	2477	418	1872	1008		
DKA in last 6 months (85%)	2314	391	1749	941		

Using this table we can determine detectable differences for each outcome/group comparison for a variety of plausible scenarios for incidence rates. Table 6-2 illustrates detectable differences assuming a two group continuity corrected chi-square test for a variety of scenarios with alpha=0.05 (2-sided).

Table 6-2. Detectable Differences in Selected Outcomes Assuming a Two-Group Continuity							
Corrected Chi-square Test for a Variety of Scenarios with Alpha=0.05 (2-sided)							
	Scenario 1: Example T1 vs. T2 Scenario 2: NHW vs. Other						
Outcome	Incidence Rate	Detectable Rate	Incidence Rate	Detectable Rate			
	for T1	for T2 (Power)	for NHW	for Other			
				Race/Ethnic			
				Group (Power)			
Hypertension	6%**	10% (80%)	6%**	10% (96%)			
	12%	18% (88%)	12%	17% (95%)			
Obese	5%	10% (90%)	9%	14% (95%)			
	10%	16% (86%)	19%	25% (91%)			
High LDL	23%	32% (84%)	14%	20% (89%)			

Section 6B - Statistical Considerations (P	hase 3 - 12/2010)
Cohort Study	

	33%	43% (85%)	24%	31% (87%)	
High ACR	9%	15% (93%)	5%	8% (86%)	
	19%	26% (87%)	10%	14% (87%)	
Hypoglycemia in last 6 months	11%	17% (90%)	23%	28% (82%)	
	21%	28% (86%)	33%	39% (88%)	
DKA in last 6 months	15%	21% (81%)	9%	13% (87%)	
	25%	32% (80%)	19%	24% (84%)	

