6.2.2. Prevalence Estimation

Unlike the incidence rate comparison, all SEARCH Cohort Study participants can be used for the prevalence rate analyses since the incident rate calculations need to remove participants who have the outcome present at visit 1 from the analyses. With this in mind we estimate that there will be 3166 participants available to contribute to prevalence rate estimates. Based on this, Table 6-3 shows a variety of scenarios for detectable differences comparing groups (i.e., type 1 vs type 2, non-Hispanic white vs others, etc) using a chi-square test to compare groups with alpha=0.05 (2-sided).

Table 6-3: Scenarios fo	or Detecting	Statistical Di	fferences	in Prevale	ence of Retinop	athy and		
Neuropathy								
Outcome	316/2849		473/2692		2112/1049 (Anticipated NHW			
				vs. Other Race Split)				
	Percentage with trait in smaller group							
	10%	20%	10%	20%	10%	20%		
	Detectable Difference (Power)							
Retinopathy	.16 (81)	.28 (86)	.15 (82)	.27 (89)	.14 (89)	.25 (88)		
	5%	15%	5%	15%	5%	15%		
Neuropathy	.10 (85)	.22 (83)	.09 (84)	.21 (85)	.08 (88)	.20 (93)		

Section 6B - Statistical Considerations (Phase 3 - 12/2010) Cohort Study

Based on this table, we see that there is 81% power to detect a difference between Type 1 and Type 2 participants on their prevalence of retinopathy: 10% in the Type 1 group and 16% or higher in the Type 2 group, a realistic potential comparison given early pilot findings of 18% of youth with evidence of DR among the first 38 evaluated.

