8.2. OVERVIEW: BACKGROUND INFORMATION

SEARCH Phase 3 will be conducted in two components, a Registry Study and a Cohort Study. Both components will be completed at all five SEARCH clinical centers, and the Coordinating Center and Central Laboratory will be the same for both components. No individual will be excluded on the basis of gender or race/ethnicity. Since the focus of this study is to learn more about the impact of diabetes on people who are less than 20 years of age at the time of diagnosis, this study includes children, adolescents, and young adults. This study does not involve fetuses, neonates, prisoners, or institutionalized individuals. Young women, who are pregnant and eligible for the study, will not be scheduled to participate in an in-person visit (IPV) until at least six weeks after the completion of the pregnancy.

The SEARCH Cohort study will involve follow-up in-person visits for all participants diagnosed in incident years 2002-2005, 2006, and 2008 in SEARCH Phases 1 and 2 and who completed a baseline visit as part of the previous SEARCH protocol that have had diabetes for at least 5 years. Youth who were eligible for a baseline visit under the previous SEARCH protocol, but who declined to participate in this in-person visit or who explicitly refused further contact or are known to be deceased; will not be asked to participate in follow up visits for this study. The IPV will involve the collection of data from medical record review (in a subset of participants), a physical examination, self-reported data on health behaviors, health care, and psychosocial factors, and the assessment of diabetic retinopathy, neuropathy, nephropathy and markers of cardiovascular disease.

A total of 3,699 youth with diabetes who were diagnosed in incident years 2002-2005, 2006, and 2008 have completed a baseline visit thus far as part of the previous SEARCH protocol. Therefore, approximately 3,700 individuals will be eligible for a follow-up in-person visit.

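### Cohort Study: the eligible count, the attendance goal and the sample sizes behind the power tables contradict each other; the effect on power is modest and depends on which count is right

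*Protocol*

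**What the plan says.** **Eligible count.** The Executive Summary (Section 1) and Section 4B, 4.1.1 both give an expected 3,699. Section 8B, 8.2 reports that 3,699 had completed a baseline visit so far and concludes that "approximately 3,700 individuals will be eligible for a follow-up in-person visit".

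**Attendance goal.** Section 5B, 5.1.1: "Our goal is to have 80% of eligible members of the cohort attend the proposed SEARCH Cohort Study visit, for a total of 3145". A further 10% are to take part by telephone or internet survey, "for a total of 90% inclusion or 3550 individuals". Table 5-1 breaks both totals down by center, type and race/ethnicity.

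**Power base.** Section 6B, 6.2: "we anticipate that at least 3,288 subjects will participate in the SEARCH Cohort Study in-person visit", with the statement that the calculations below use it. Section 6B, 6.2.2 says all Cohort participants can be used for prevalence, yet "we estimate that there will be 3166 participants available to contribute to prevalence rate estimates". Table 6-4 uses 2,711 type 1 and 450 type 2 participants, a total of 3,161.

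**Splits.** Section 6B, 6.2.1: "proportion in subgroups are 86% versus 14% (the proportions of T1D and T2D"), and 65% versus 35% for non-Hispanic white (NHW) versus all others.

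**The concern.** A power analysis should trace back to one eligible count multiplied by one attendance rate. Here at least five totals are in play (3,699, 3,145, 3,288, 3,166 and 3,161), and no single rate links them. The figure offered as a floor for attendance is higher than the attendance goal. The power text also says that one number underlies the tables, while the tables use another for most cells.

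The type 2 group limits every type 1 versus type 2 comparison, and its Table 6-1 column is the one computed from the largest base. At stake is whether a reader can tell which sample size supports Section 6B, and whether comparisons presented as having 80% power have it.

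**Working it through.** **1. Do the totals reconcile?**
- 0.80 × 3,699 = 2,959; 0.90 × 3,699 = 3,329.
- 3,145 / 0.80 = 3,931; 3,550 / 0.90 = 3,944. Neither eligible count appears anywhere in the protocol.
- 3,145 / 3,699 = 85.0%; 3,550 / 3,699 = 96.0%; 3,166 / 3,699 = 85.6%; 3,288 / 3,699 = 88.9%.
- 3,288 / 0.80 = 4,110 eligible would be needed.

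**2. Which base does Table 6-1 use?** Implied base = cell / (share free of the condition × subgroup share).

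| Outcome (free at first visit) | T1D 86% | T2D 14% | NHW 65% | Other 35% |
|---|---|---|---|---|
| Hypertension (92%) | 3,165 | 3,284 | 3,166 | 3,165 |
| Obesity (76%) | 3,166 | 3,280 | 3,166 | 3,165 |
| High LDL (57%) | 3,082 | 3,283 | 3,166 | 3,163 |
| High ACR (90%) | 3,165 | 3,286 | 3,166 | 3,165 |
| Hypoglycemia (91%) | 3,165 | 3,281 | 3,165 | 3,165 |
| DKA (85%) | 3,166 | 3,286 | 3,166 | 3,163 |

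Only the T2D column rests on 3,288. For example, 0.92 × 0.14 × 3,288 = 423 as printed, against 408 at 3,166. As a result, the same hypertension-free set sums to 2,504 + 423 = 2,927 in Scenario 1 and 1,893 + 1,019 = 2,912 in Scenario 2. The T1D LDL cell (1,511) should be 1,552 at 3,166 or 1,612 at 3,288.

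**3. Reproducing Table 6-2.** Two-proportion normal approximation, continuity-corrected, two-sided alpha 0.05:

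power = Φ{ [ |p1 − p2| − ½(1/n1 + 1/n2) − 1.96·SE0 ] / SE1 }, with SE0 from the pooled rate and SE1 from the separate rates.

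Hypertension 6% vs 10%, n = 2,504 and 423: pooled rate 0.0658, SE0 = 0.01303, SE1 = 0.01534, correction 0.00138. This gives (0.04 − 0.00138 − 0.02554) / 0.01534 = 0.852, so power is 80.3% (stated 80%). All 24 stated powers reproduce within about 1 point at the printed cell sizes.

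**4. Other bases, printed splits kept.** The three comparisons most affected, all T1D vs T2D:

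| Comparison | Stated | At printed n | 3,166 | 3,145 | 2,959 |
|---|---|---|---|---|---|
| Hypertension 6% vs 10% | 80 | 80.3 | 79.2 | 78.9 | 76.5 |
| DKA 15% vs 21% | 81 | 81.2 | 80.0 | 79.7 | 77.3 |
| DKA 25% vs 32% | 80 | 80.3 | 79.0 | 78.7 | 76.2 |

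Over all 24 comparisons, the largest shortfall at 3,145 is about 1.3 points. At 2,959 every power is below the stated value, by 0.9 to 3.8 points. Fifteen fall short by more than 2 points, and the 21 not shown lie between 80.1% and 95.1%.

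**5. Tables 6-3 and 6-4.** The Table 6-3 groups total 3,165, 3,165 and 3,161. Scaled in proportion to 2,959, two of the 12 powers drop below 80% (78.3 against a stated 81; 79.8 against 82). For Table 6-4, the systolic pressure difference at r = .50 is 12.7 × √0.75 × (1.96 + 0.84) × √(1/2,711 + 1/450) = 1.57 mmHg, as printed. At 2,959 it is 1.62 mmHg with the same split, or 1.64 mmHg with the Table 5-1 mix (about 2,550 and 409).

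**6. Splits.** Table 5-1 gives T2D 107 + 328 = 435, which is 13.8% of 3,145. Race/ethnicity other than NHW is 700 + 328 = 1,028, which is 32.7% rather than 35%.

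**The case against.** The strongest reply is that the contradiction does not show a loss of power. A reader might infer that the stated powers will not be delivered. That follows only if 3,699 is the correct base for the 80% goal. The protocol also prints the goal as 3,145, with a full breakdown, and at 3,145 the stated powers hold to within about 2 points. The text does not settle which figure is wrong. This objection stands.

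Four further inferences are tempting but not supported:
- *That 3,699 is a ceiling.* Section 8B, 8.2 describes it as the count completed so far. Although Sections 1 and 4B call it the expected number, the text does not exclude later additions.
- *That 75% attendance is a lower bound.* Section 6B, 6.1.3 says "75% of the 2002-2005 incidence cases have at least 2 in-person visits". This describes earlier visits in some of the incident years. It is not a forecast for this visit, for which Section 5B, 5.1.2 describes added retention measures and higher remuneration.
- *That a fourth Table 6-2 comparison falls below 80%.* Hypoglycemia 23% vs 28% (NHW vs Other) is 80.1% at 2,959 with the printed 65/35 split. It reaches 78.8% only if the race split is changed as well.
- *That every figure in Section 6B depends on 3,288.* Most cells do not use it. The type 1 versus type 2 retinopathy example in 6.2.2 uses a smaller group of only 316. With 409 and 2,550, 10% vs 16% has about 90-91% power, above the stated 81%.

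DKA and hypoglycemia are also self-reported. If the telephone and internet surveys carry those items (an assumption), 3,329 could apply to them. The two DKA comparisons would then be 81.9% and 81.0% with the 86/14 split. Section 6.2, however, bases its number on the in-person visit.

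Finally, Section 6B presents its figures as illustrative examples, and the cohort invites everyone eligible, so no enrolment target turns on a few points of power. This limits the severity but does not reconcile the numbers.

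**Conclusion.** The inconsistency is established from the protocol's own figures. The eligible count, the 80% and 90% totals and the power base cannot all be right; the stated attendance floor exceeds the stated goal; and Table 6-1 mixes two bases and contains one cell that matches neither.

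The consequence for power is modest and conditional. If 3,145 is right, the loss is at most about 1.3 points, and three type 1 versus type 2 comparisons stated at 80-81% become 78.7-79.7%. If 80% of 3,699 is right, all 24 Table 6-2 powers fall by about 1 to 4 points, those three become 76.5%, 77.3% and 76.2%, and the detectable systolic difference at r = .50 rises from 1.57 to about 1.62-1.64 mmHg.

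The Table 6-2 results assume the continuity-corrected test the protocol names, the printed baseline-free percentages and the printed 86/14 and 65/35 splits. The point deserves correction because the figures are the plan's stated sample-size basis. It does not threaten the study.

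**What to change.** - State one eligible count and one in-person attendance rate, and derive every total from them. If 3,699 and 80% are kept, the in-person total is 2,959 and the 90% total is 3,329. If 3,145 is intended, state the eligible count that produces it (about 3,930) and correct Sections 1, 4B and 8B.
- Bring Section 5B, 5.1.1 with Table 5-1, Section 6B, 6.2 (3,288) and Section 6B, 6.2.2 (3,166) into line with that choice.
- Recompute Tables 6-1 to 6-4 from the single base, including the T2D column and the T1D LDL cell of Table 6-1. Use type and race/ethnicity splits that agree with Table 5-1.
- Restate the powers and detectable differences that follow.

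The cost is protocol wording and a re-run of four tables. Some stated powers become a few points less favourable. Design, visits and data collection do not change.
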